^h Tests related to inclusion exclusion criteria should be performed at screening visit. Neutrophil count, Platelet count, Total bilirubin, ALT, AST, Creatinine, Creatinine, Creatinine clearance, PTT, PT, INR. All the other clinical chemistry and hematology are mentioned in Section 10.2, Table 10-1.

PROMIS, Self-Efficacy Assessment, and GODIN survey are not mandatory if translated version in not available. Questionnaires required are detailed in Section 10.4.

^j Assessment to be done in triplicate.

Page: 23 of 86

Table 1–4: Schedule of Activities Randomized Phase

STUDY			TREATMENT Period								
STUDY ELEMENT/PERIOD	Screening	Baseline		Treatment Period: Weeks							
VISIT acceptable time window (days)	(Up to 28 days before Week 1 Day 1)	(up to 7 days beforeW eek1 Day 1)	2 [± 7 d]	4 [± 7 d]	8 [± 7 d]	12 [± 7 d]	16 [± 7 d]	24 [± 7 d]	36 [± 7 d]	52 [± 7 d]	EOT 30 days (+7 days) after last dose ^c
PROCEDURE											
Informed consent	х										
General											
Demography		Х									
Inclusion and exclusion criteria	х										
Relevant medical history (Includes substance use)		х									
PC history, classification (diagnosis, staging) including pre-treatments		x									
Prior/Concomitant medications ^d	х						χ ^g				
CT/ MRI/ PSMA-PET bone scan ^a	х										
Randomization		Х									
Physical examination											
Full physical examination		Х									Х
Safety											
AE /SAE/ discontinuation due to AEs ^b						Xg					х
ECOG performance status	Х	Х		Х		Х		Х		Х	
Fasting glucose, fasting insulin, hemoglobin A1C, lipid profile, lean body massf, fat massf, weight		х		х		x		х	х	х	х
Clinical chemistry (liver), hematology	X ^h	х		х		х		х	х	х	х
DHT, DHEA, SHBG, androstenedione, prolactin, estradiol		х		x		х		х	х	х	х
12-lead ECG ^j		Х		Х						х	х
Vital signs	Х	Х	Х	х	Х	х		Х	Х	Х	Х

Page: 24 of 86

											1 450.
STUDY			TREATMENT Period								
STUDY ELEMENT/PERIOD	Screening	Baseline				Treatment	Period: Weeks	5			
VISIT acceptable time window (days)	(Up to 28 days before Week 1 Day 1)	(up to 7 days beforeW eek1 Day 1)	2 [± 7 d]	4 [± 7 d]	8 [± 7 d]	12 [± 7 d]	16 [± 7 d]	24 [± 7 d]	36 [± 7 d]	52 [± 7 d]	EOT 30 days (+7 days) after last dose ^c
Bone specific alkaline phosphatase (BSAP) and CTX		х		х		х		х	х		
Efficacy											
Testosterone, free testosterone	х	х	х	х	х	х	х	х	х	х	х
Serum PSA	х	х	Х	х	х	х	х	Х	х	х	Х
Gonadotropins, LH, FSH		х	Х	х	х	х	х	Х	х	х	Х
24 DEXA scan		х								х	
Study treatment dispensinge		х		х		х		х	х		

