Patient reported outcomes											
FACT-P		Х		Х		х		Х	Х	х	Х
Surveys: physical function ⁱ		х				x		Х		x	

^a Radiological tumor assessments will be conducted only at screening to exclude presence of visceral metastases, and because these are not considered standard of care, will only be done at other times based on treating physician discretion and based on PSA progression. Investigators are encouraged to provide the results of PSMA-PET CT scans in the eCRF if performed (optional at baseline or during the study).

If patient treatment discontinued BEFORE completing the full 52-week treatment, please refer to the Active Follow Up Period SoA Table 1-5.

Bayer will provide questionnaires wherever validated version is available in the said language.

Abbreviations: A1C (hemoglobin) Glycated, AE adverse event, ALT Alanine aminotransferase, AST Aspartate aminotransferase, BSAP bone-specific alkaline phosphatase, CT computerized tomography, CTX C-telopeptide, DEXA dual energy x-ray absorptiometry, DHEA dehydroepiandrosterone, DHT dihydrotestosterone, ECG Electrocardiogram, ECOG Eastern Cooperative Oncology Group, EOT end of treatment, FACT-P Functional Assessment of Cancer Therapy – Prostate Cancer, FSH follicle-stimulating hormone, INR international normalized ratio, LH-luteinizing hormone, MRI magnet resonance imaging, PC prostate cancer, PSA Prostate-specific antigen, PSMA-PET Prostate-specific membrane antigen positron emission tomography, PT prothrombin time, PTT partial thromboplastin time, SAE serious adverse event, SHBG sex hormone-binding globulin, SOC standard of care.

^b Safety assessments should be continued as per SOC at time of progression. After the 30-day short term follow-up period, only SAEs that are considered related to study intervention or study participation, with concomitant medications used to treat the event, should be reported by the investigator. Documentation of progression should be provided to the Sponsor (in CRF).

^c During the treatment period and up to 30 days following study intervention discontinuation, all (S)AEs are collected, regardless of causality.

d For anti-cancer therapies, also collect prior to 28 days.

^e Treatment compliance will also be assessed at each visit when study intervention is dispensed.

f Bioelectrical impedance scale to be used.

⁹ To be collected and updated as needed, not visit dependent. Eligibility assessments need to be completed prior to the patient being enrolled to the study.

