1.1. Objectives, Endpoints, and Estimands

Table 1-1: Lead-in phase objectives and Endpoints

Objectives	Endpoints
Primary	
To evaluate the impact of darolutamide	Change in serum testosterone level from
on serum testosterone level	baseline to week 12
over a 12-week intervention period	
Secondary	
To evaluate the impact of darolutamide	Change in serum testosterone level from
monotherapy on serum testosterone level over	baseline at week 24 and 52
the course of a 52-week intervention period	
Assess PSA response rate	Serum PSA Week 4, 12, 24, 36, 52
To assess safety of darolutamide monotherapy	AE assessments using NCI CTCAE (v.5.0)
in participants with hormone-naïve prostate	
Cancer with BCR	

Abbreviations: BCR-Biochemical Recurrence, NCI CTCAE-National Cancer Institute Common Terminology Criteria for Adverse Events, PSA Prostate Specific Antigen.

Table 1-2: Randomized Phase Objectives and Endpoints

Objectives	Endpoints	
Primary		
To compare the effects of treatment with darolutamide vs. enzalutamide monotherapy on serum testosterone level over a 12-week intervention period	Change in serum testosterone level from baseline to week 12	
Secondary		
To compare the effect of darolutamide vs. enzalutamide monotherapy on serum testosterone level over the course of a 52-week intervention period	Change in serum testosterone level from baseline at week 24 and 52	
Measure changes in markers of endocrine function related to sex hormones	Changes in the blood levels of sex hormones (DHT, DHEA, SHBG, LH, FSH, Androstenedione, Prolactin, Estradiol)	
Measure changes in markers of components of fat and glucose metabolism	Changes blood levels of Total cholesterol, High- density and low-density lipoproteins, Triglycerides, Haemoglobin A1C, Fasting insulin, Fasting glucose, Fat body mass, Lean body mass	
Assess PSA response rate	Serum PSA Week 4, 12, 24, 36, 52	
To assess safety and QOL of darolutamide vs. enzalutamide monotherapy in participants with hormone-naïve prostate Cancer with BCR	AE assessments using NCI CTCAE (v.5.0) and FACT-P	
Exploratory		
Evaluate changes in Bone turnover	Markers of bone turnover: BSAP, CTX, DEXA scan	
Physical function*	Subjective physical function: Godin – 4 questions, PROMIS Fatigue – 8 questions, PROMIS Physical – 6 questions, Self- Efficacy – 9 questions	

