4.1. General Considerations

All baseline variables will be reported using the appropriate statistics: categorical variables by frequency tables (frequencies and percentages) and continuous variables by sample statistics (i.e., mean, standard deviation, minimum, median, quartiles, and maximum). The number of participants screened will be summarized for both the lead-in and randomized cohorts.

The efficacy related endpoints will be evaluated in the evaluable population while the safety endpoints will be evaluated in the safety population.

Efficacy endpoints will consider data until last dose of study drug (while on treatment).

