4.3.1.2 Randomized Phase

• Testosterone at weeks 24 and 52:

The differences between the log transformed data at the visit and baseline will be compared across treatment groups with 95% Confidence Intervals using SAS PROC MIXED with the SLICE option and a Toeplitz covariance structure. These will be

ARAMON V3.0 Page: 16 of 31

transformed to the ratio of the fold change from baseline for darolutamide to that for enzalutamide and 95% confidence intervals using the same steps as for the primary analysis in the randomized phase. SAS code will be similar to code shown in Appendix 6: Randomized phase analysis for natural logarithm transformed Testosterone and other endpoints using the log transformation. Results will be summarized in a similar manner to the primary endpoint and will be summarized graphically using the mean percent change over time with 95% confidence intervals at each visit by treatment group, flagging visits where differences are significant at the nominal 0.05 and 0.01 levels.

• Sex hormones:

Will be analyzed at week 4, 12, 24 and 52 similar to testosterone.

• Components of fat and glucose metabolism:

Will be analyzed at week 4, 12, 24 and 52 similar to testosterone.

PSA responses

Will be compared descriptively across treatments at weeks 4, 12, 24, 36 and 52 using frequencies and percentages.

• FACT-P

Differences in the FACT-P prostate cancer subscale and total will be summarized at each visit using PROC Mixed with the SLICE option, and the mean subscale and total scores will be depicted graphically over time with 95% confidence intervals at each visit by treatment group, flagging visits where differences are significant at the nominal 0.05 and 0.01 levels. The scoring procedure for FACT-P is elaborated in Appendix 2: Scoring procedures for FACT-P.

• Analysis of AEs:

All grades of the feminizing side effects of gynecomastia (including breast enlargement, breast mass, breast swelling), breast tenderness/pain, nipple pain, and hot flush, will be summarized using frequencies and percentages by treatment group.

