4.4. Other Exploratory Endpoints

• Markers of bone turnover:

Will be analyzed for the randomized phase as described for the sex hormones and components of fat and glucose metabolism in Section 4.3.1.2.

• Physical function measures:

Will be summarized graphically as described for the FACT-P subscale in Section 4.3.1.2. The scoring procedures for PROMIS physical function questionnaires are elaborated in Appendix 3: Scoring for PROMIS.

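### Randomized-phase schedule omits BSAP/CTX at week 52, so the exploratory week-52 arm comparison of these two markers cannot be made as planned

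*Protocol*

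**What the plan says.** Bone turnover is an exploratory objective of the randomized phase only. SAP 1.1, Table 1-2 defines the endpoint as "Markers of bone turnover: BSAP, CTX, DEXA scan", and Protocol Table 3-2 agrees. The lead-in objectives (Protocol Table 3-1, SAP Table 1-1) list no bone endpoint.

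Protocol 8.4 gives no sampling times of its own and refers to the schedule. Protocol 1.5 has three schedules, each with a row labelled "Bone specific alkaline phosphatase (BSAP) and CTX": Table 1-3 for the lead-in phase, Table 1-4 for the randomized phase, and Table 1-5 for active follow-up. The notes to Tables 1-3 and 1-4 say who moves to the third: "If patient treatment discontinued BEFORE completing the full 52-week treatment, please refer to the Active Follow Up Period SoA Table 1-5".

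For the analysis, Protocol 9.4.3 defers to the SAP. SAP 4.4 says of the bone-turnover markers: "Will be analyzed for the randomized phase as described for the sex hormones and components of fat and glucose metabolism in Section 4.3.1.2". In SAP 4.3.1.2 the sex hormones and the metabolic components each carry the same instruction: "Will be analyzed at week 4, 12, 24 and 52 similar to testosterone". The testosterone method referred to there is a comparison of log change from baseline, "compared across treatment groups with 95% Confidence Intervals using SAS PROC MIXED with the SLICE option and a Toeplitz covariance structure".

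**The concern.** The SAP appears to plan a between-arm comparison of BSAP and CTX at a visit where the randomized-phase schedule takes no sample from participants still on treatment. The pattern across the tables is the reverse of what the objectives would suggest. The lead-in phase, which has no bone objective, is sampled at week 52, and so are participants who stop treatment early. Randomized participants who complete treatment are not.

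At stake is the last of four analysis times for two of the three components of this endpoint, in the only randomized comparison the trial makes. A gap in the SAP text can be repaired before database lock. A blood sample that was never taken cannot.

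**Working it through.** This is a check of schedule against analysis plan. No sample-size or power figure enters it, and the plan gives no figure to reproduce.

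**Step 1. Read the schedule rows.** The visit columns in Tables 1-3 and 1-4 are screening, baseline, weeks 2, 4, 8, 12, 16, 24, 36, 52 and EOT, 11 in all. Table 1-5 has eight, from week 2 to week 52.

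| Row | Cells | Visits marked |
|---|---|---|
| Table 1-4, BSAP/CTX | 11 | baseline, 4, 12, 24, 36 |
| Table 1-3, BSAP/CTX | 11 | baseline, 4, 12, 24, 36, 52, EOT |
| Table 1-5, BSAP/CTX | 8 | 4, 12, 24, 36, 52 |
| Table 1-4, sex hormones (DHT row) | 11 | baseline, 4, 12, 24, 36, 52, EOT |
| Table 1-4, FACT-P | 11 | baseline, 4, 12, 24, 36, 52, EOT |
| Table 1-4, DEXA | 11 | baseline, 52 |
| Table 1-4, drug dispensing | 11 | baseline, 4, 12, 24, 36 |

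**Step 2. Is the blank real?** The BSAP/CTX row of Table 1-4 keeps its full 11 cells, so the marks align with the columns. The other Table 1-4 assessment rows checked above keep their week-52 marks. The pattern is identical to the dispensing row of the same table, where a blank at week 52 is expected. A true blank is the better reading, although a mark lost in reading the PDF cannot be wholly excluded.

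**Step 3. Compare with the analysis visits.** The visits inherited from SAP 4.3.1.2 are 4, 12, 24 and 52. The post-baseline visits collected under Table 1-4 are 4, 12, 24 and 36. Weeks 4, 12 and 24 match. Week 52 is analysed but not collected, and week 36 is collected but not analysed. With visit windows of ±7 days, the week-36 sample cannot stand in for week 52.

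**Step 4. Count the week-52 values.**

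- On treatment: 0 of 20 per arm, so 0 of 40.
- Off treatment, under Table 1-5: the documents give no rate of stopping treatment before week 52. Assuming 0% to 20%, the count is 20 × 0 = 0 to 20 × 0.20 = 4 per arm, all of them off drug.

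**Step 5. What the model can give.** SAP 4.1 restricts some analyses: "Efficacy endpoints will consider data until last dose of study drug (while on treatment". If that rule is applied to BSAP and CTX, no week-52 record remains and the week-52 treatment contrast cannot be estimated. If it is not applied, the contrast rests only on the few participants who had stopped the drug, and it cannot be estimated if either arm has none. Neither is the planned comparison.

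**The case against.** The strongest reply is that SAP 4.4 imports a method and not a list of visits. It names no visits for the bone markers, and the list in SAP 4.3.1.2 cannot apply literally to the whole endpoint, because DEXA is part of it and is done only at baseline and week 52. On that reading BSAP and CTX are analysed wherever they were collected. This stands in part: the week-52 plan for BSAP and CTX follows from a cross-reference and is not stated outright. It does not explain why early discontinuers and the lead-in phase are sampled at week 52 while randomized completers are not, and the documents give no reason. Even on this reading SAP 4.4 needs the visits stated.

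It is also fair that the randomized phase is conditional on the lead-in results, that its design may change, and that SAP 4.6.1 foresees changes to data collection. That gives an opportunity to correct the table, but does not correct it.

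A reader might infer more than the documents support:

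- **That the whole week-52 bone comparison is lost.** DEXA keeps its week-52 mark in Table 1-4.
- **That the on-treatment rule certainly discards the discontinuers' values.** The rule names efficacy endpoints, and Tables 1-3 and 1-4 list BSAP/CTX under Safety. The SAP introduction counts bone mineral density among efficacy outcomes but does not name these two markers. The exclusion is conditional.
- **That a planned joint reading of markers and bone density is lost.** No section plans one.
- **That the blank at EOT is a second gap.** No planned analysis uses an EOT bone marker.

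**Conclusion.** The inconsistency is real and the plan is wrong as written on this point. Table 1-4 schedules no week-52 BSAP or CTX for participants still on treatment, while SAP 4.4, through SAP 4.3.1.2, compares the arms at week 52. One of four analysis times is lost for two of the three bone-turnover components.

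Severity is minor. The endpoint is exploratory, and the primary and secondary endpoints are untouched. The conclusion rests on two assumptions: that the blank in Table 1-4 is in the original document, which the sponsor can confirm at sight, and that the cross-reference in SAP 4.4 carries the visits as well as the method.

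**What to change.** Mark BSAP/CTX at week 52 in Table 1-4, as in Tables 1-3 and 1-5. Blood is already drawn at that visit for testosterone, PSA and the other hormones, so the cost is one schedule entry and a small laboratory charge. No EOT mark is needed for any planned analysis.

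If the omission is deliberate, leave the table and state in SAP 4.4 that BSAP and CTX are compared only at the visits collected, saying whether week 36 is one of them. That costs one sentence and gives up the week-52 marker comparison openly.

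With the first option, SAP 4.4 should also say whether the on-treatment rule of SAP 4.1 covers these markers, so that the handling of week-52 values from early discontinuers is settled before the data are seen.

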2.1 Study Rationale

The study of care for men with biochemically relapsed prostate cancer in the United States annually, is an estimated 40,000 - 50,000, with treatment of these subjects with this disease state being far from standardized.

2.2 Background

Prostate cancer is the second most common cancer in men worldwide, with an estimated incidence of 900,000 cases and 258,000 deaths in 2008 (Fizazi et al. 2020). In the United States, approximately 222,000 cases were diagnosed in 2010 (Jemal et al. 2011), of which an estimated two-thirds undergo radical prostatectomy or definitive radiation therapy (RT). Approximately 25%-35% of patients treated with definitive surgical or radiation therapy for localized adenocarcinoma of the prostate will recur in the form of rising serum PSA without overt metastatic disease, termed biochemical recurrence (BCR) (Jemal et al. 2010, Zietman et al. 2004). An estimated 40,000 - 50,000 men in the U.S. develop biochemically relapsed prostate cancer each year, yet treatment of men in this disease state is far from standardized. The optimal time to initiate treatment and the choice of specific therapy for such patients remains controversial and highly variable in clinical practice. This may be due to several potential reasons, including (1) absence of prospective randomized trial data demonstrating an overall survival advantage for one therapeutic approach and (2) a biologically heterogeneous population with a variable natural disease course.

Biochemical recurrence (BCR) of prostate cancer, characterized by a rising prostate-specific

Page: 27 of 86

antigen (PSA) after definitive primary therapy, occurs in approximately 20-40% of post-prostatectomy patients and 30-50% of post-radiation patients within 10 years (Artibani et al. 2018). While many patients with BCR do well clinically for years, proper treatment of BCR is important as BCR precedes the appearance of clinical metastasis by 8 years after radical prostatectomy (RP) and by 7 years after primary definitive RT (Artibani et al. 2018).

The kinetics of PSA change over time has emerged as an important independent prognostic factor for patients with BCR, both with respect to time to development of metastases as well as the risk of prostate cancer-specific mortality. In a cohort study of 8,669 men treated with localized therapy, of the 1,451 men with PSA recurrence, a PSA doubling time (PSADT) less than 3 months was associated with an approximately 50% chance of prostate-cancer specific mortality at 5 years; in contrast, those with a PSADT greater than 12 months had less than 10% prostate cancer-specific mortality during the same time interval (Han et al. 2003). In another study of 1,650 patients previously treated with external beam radiotherapy, at the time of PSA recurrence, the 3-year risk of distant metastases for a PSADT of 0-3 months, 3-6 months, 6-12 months, and > 12 months was 49%, 41%, 20%, and 7%, respectively (P <0.001) (D'Amico et al. 2004).

Risk stratifying patients with biochemical recurrence may allow for more optimal and individualized selection of treatment (Zelefsky et al. 2005).

Various management options are acceptable for prostate cancer with BCR, including observation, intermittent or continuous use of androgen deprivation therapy (ADT), nonsteroidal antiandrogen (NSAA) therapy, and salvage radiotherapy or surgery.

A prolonged PSADT, as well as other factors such as low Gleason grade, positive surgical margins, and pre-treatment PSA level < 2.0 ng/mL, may help to predict which patients may benefit from localized salvage therapy such as radiotherapy after prior prostatectomy (Ryan and Small 2006).

For those patients with a PSADT greater than 12 months, active surveillance may be the optimal treatment approach, especially in elderly patients with other potentially life-limiting comorbidities who are not candidates for locally directed salvage therapy. For patients with a shorter PSADT, who are at significant risk of prostate-cancer specific mortality over the next 5-10 years, early treatment with continuous androgen deprivation therapy (ADT), in the form of luteinizing hormone releasing hormone (LHRH) antagonists or agonists (e.g., goserelin, leuprolide acetate) with or without a first generation androgen receptor (AR) antagonist (e.g., flutamide, bicalutamide), has been a standard approach. In that patient population, intermittent ADT is also considered an alternative approach, which showed non-inferiority to continuous ADT with respect to survival and improved quality of life (National Comprehensive Cancer Network 2021).

Page: 28 of 86

Androgen deprivation therapy (ADT) constitutes the current first line systemic treatment for prostate cancer, resulting in marked suppression of serum testosterone levels and associated loss of libido and sexual function (DiBlasio et al. 2008). ADT also has well documented metabolic adverse effects including decreased bone mineral density, loss of muscle mass, increased lipid levels, and insulin resistance leading to a higher risk of diabetes and contributing to an increased risk of cardiovascular disease (Jespersen et al. 2014, Taylor et al. 2009). Attempts to reduce the morbidity of advanced prostate cancer treatments with less adverse effect have largely focused on non-testosterone lowering strategies using first generation non-steroidal anti-androgen (NSAA) monotherapies, an approach that is supported by EAU Guidelines on Prostate cancer (Mottet et al. 2020) and largely based on benefits in health-related quality of life (HRQoL) and tolerability.

For patients who are treated with systemic therapy, NSAAs serve as an alternative to ADT by providing a potentially more favorable side effect profile. In contrast to ADT, NSAAs are associated with increased bone mineral density and reduced risks of fat accumulation, hyperglycemia, anemia, fatigue, loss of libido, and vasomotor flushing.

Second generation antiandrogens (enzalutamide, apalutamide and darolutamide) have demonstrated increased efficacy compared to first generation antiandrogens (Rice et al. 2019). Such agents to date remain a part of the SOC for men with advanced prostate cancer.

The effect of monotherapy with ARIs enzalutamide and apalutamide in patients with biochemical recurrence has been explored and reported. A single arm, phase 2 study by Tombal et al evaluating enzalutamide monotherapy in biochemically recurrent and metastatic patients showed similar PSA level reduction by enzalutamide monotherapy compared to testosterone suppression by LHRH analogues. Enzalutamide alone, however, resulted in a mean increase of testosterone levels at week 25 of 114% with very frequent side effects of grades 1-2 such as gynecomastia (36%), fatigue (31%), nipple pain (19%), and hot flush (18%) (Tombal et al. 2014). In this enzalutamide study, peak serum testosterone rise plateaued at around 10 to 13 weeks of treatment.

(Maluf et al. 2018) presented data of LACOG 0415, a three-arm phase 2 study exploring efficacy of the ADT-free alternatives in a patient population with advanced hormone-sensitive prostate cancer and biochemical recurrence. The apalutamide monotherapy arm demonstrated similar PSA decline level to the other two arms, however, it too resulted in a high mean increase in levels of testosterone of 134.3% at week 25 with high incidences of any grade side effects such as gynecomastia (55%), rash (26%), fatigue (21%), pruritus (17%) and breast pain (14%). In this apalutamide study, peak serum testosterone rise plateaued at around 10 to 13 weeks of treatment.

The increase in serum testosterone level observed with enzalutamide and apalutamide is thought to result from the ability of these compounds to penetrate the blood-brain-barrier (BBB), resulting in negative feedback on the luteinizing hormone (LH)-testosterone axis and subsequent rise in testosterone. Unfortunately, it is not fully established whether this negative feedback loop occurs entirely within the central nervous system (CNS) or whether parts of it may be situated outside of the BBB.

Page: 29 of 86

Penetration of the BBB by apalutamide and enzalutamide may also result in added CNS related side effects, including fatigue, falls, cognitive impairment, and impaired balance, as evidenced in phase 3 clinical studies.

Darolutamide does not appear to experience the above-mentioned pharmacokinetic limitations, given that it has a distinct chemical structure with high binding affinity to the androgen receptor with a low blood brain barrier penetration (Zurth et al. 2018, Zurth et al. 2019). Evidence from clinical studies including the ARAMIS phase 3 trial in nmCRPC suggests a reduction in CNS related side effects like fatigue, falls, cognitive decline and memory impairment, as well as other side effects commonly seen with other ARIs like fractures, rash and hypertension (Fizazi et al. 2019, Moilanen et al. 2015).

Darolutamide has demonstrated lower penetration of the BBB compared to enzalutamide and apalutamide in preclinical models (Zurth et al. 2018, Zurth et al. 2019). Additionally, enzalutamide but not darolutamide reduced blood flow in brain areas related to cognitive function in an imaging study conducted in healthy volunteers (Williams et al. 2020).

Due to the low BBB, darolutamide is expected to lead to a reduced reactive testosterone rise via the hypothalamic-pituitary gland-gonadal axis, which in turn is expected to result in significantly less peripheral conversion of testosterone to estrogen and the related feminization side effects. In consequence darolutamide used as monotherapy may have high efficacy against prostate cancer, coupled with a favorable short- and long-term side effect profile and therefore may potentially disrupt the dogma of testosterone reduction as foundational therapy in prostate cancer

Earlier use of ADT may be better than delayed therapy, although the definitions of early and late (i.e., what level of PSA) remain controversial (National Comprehensive Cancer Network 2021). The multicenter phase 3 TROG 03.06/VCOG PR01-03 (TOAD) trial randomized 293 men with PSA relapse after operation or radiation (n=261) or who were not considered for curative treatment (n=32) to immediate ADT or ADT delayed by a recommended interval of more than 2 years (National Comprehensive Cancer Network 2021). Five-year OS was improved in the immediate therapy arm compared with the delayed therapy arm (91.2% vs 86.4%, log-rank P=0.047) (National Comprehensive Cancer Network 2021). However, the hormone-treatment related symptoms were higher in the immediate ADT group compared with the delayed ADT group (National Comprehensive Cancer Network 2021). Hence, the current NCCN guidelines v2.2021 for prostate cancer state that the benefit of early ADT must be balanced against the risk of ADT related side effects and ADT should be considered earlier in patients with an elevated PSA and/or a shorter PSADT and an otherwise long-life expectancy.

